Choice of NTT in children requiring NTI for dental procedures has no impact on the degree of nasal mucosal injury.

Primary Outcome:

Mucosal damage as quantified by presence and severity of bleeding immediately after passage of the NTT through the nasopharynx.

Secondary Outcomes:

Presence and degree of impingement of the NTT during NTI.

Postoperative epistaxis as defined as ongoing nasal bleeding in the recovery unit (PACU), presence of post-extubation croup in the PACU, and time to discharge from the PACU.

Research Protocol:

Inclusion criteria: children between the ages of 3-11, ASA 1-3, presenting to Wolfson's Children's Hospital (WCH) for dental procedures requiring general anesthesia with NTI.

Exclusion criteria: ASA >3, known bleeding disorder, recent or ongoing treatment with blood-thinning medicines, frequent epistaxis, active URI/congestion/rhinorrhea, craniofacial abnormalities prohibiting NTI, known difficult airway, prior nasal surgery/trauma, or allergies to any of the medicines used in this study.

Preop: eligible patients will be identified by their dentist and receive a brochure detailing the study during their dentist visit. Eligibility will be confirmed by one of the study investigators or selected research personnel (study nurse/nurse practitioner) on the day of surgery and consent obtained with the parents.

Preoperative anxiolysis will be at the discretion of the anesthesiologist, but should be limited to oral or intravenous midazolam, dexmedetomidine, or intramuscular ketamine, and not include any medicines administered intranasally.

Intraop: cases are assigned exclusively to one of the study investigators, but may involve the presence of trainees (anesthesia residents, fellows or assistants).

Induction: pre-oxygenation followed by mask induction using 6-8% Sevoflurane in Nitrous oxide/O₂ (60/40) followed by IV placement (22-24g), Fentanyl 1mcg/kg, Propofol 1-3mcg/kg, Rocuronium 0.6mg/kg.

Nasal Prep: Oxymetazoline (Afrin, Merck Consumer Care, Inc) nasal spray, 1 pump each nostril. Using the smallest pediatric sized flexible fiberoptic scope, nostril patency and degree of choanal obstruction (as defined by adenoid size, which is known to vary by patient age (8,9,10)) will be assessed avoiding tactile trauma to the nasal mucosa. Unless it is deemed not patent or significantly diminished in size, the R nostril will be preferably selected for intubation as most standard NTT are designed in favor of R-sided NTI.

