Postop: in the recovery unit (PACU), presence of persistent epistaxis, post-extubation croup, and the time to discharge from PACU will be noted.

Research Plan:

This will be a prospective, randomized controlled trial in children aged 3-11yrs undergoing dental procedures at WCH. We are looking to exclude the null hypothesis of no effect of NTT design by observing significant differences in the above-mentioned primary- and secondary outcome variables in the study-vs. control groups. A sample size of 80 patients (40 in each group) can detect the difference of the same magnitude between our study and control groups with a power of more than 98% at the level of significance of 0.05. Randomization to study (Parker NTT) vs. control (Standard NTT) will be computer generated and will be stratified by adenoid size. (Please refer to the Statistics Section below)

Recruitment will be facilitated by brochures handed out by our participating dental surgeons, and final enlistment will be done on the day of surgery.

Statistics Description:

Power and Sample Size Justification: The primary aim of the study is to compare the proportion of patients with the presence of at least mild (as defined in the intubation procedure section) bleeding between Parker NTT (study) and Standard NTT (control) groups. To our knowledge, no studies reported conducting research to assess the impact of mucosal injury in pediatric patients. A pediatric study (ref: El-Seify et al) reported a significant difference in the proportion of patients with the presence of bleeding between the control group (27.5%) and a similar method of our study group (7.5%). A sample size of 80 patients (40 in each group) can detect the difference of the same magnitude between our study and control groups with a power of more than 98% at the level of significance of 0.05. Randomization will be stratified by adenoid size.

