Data Analysis: Collected data will be summarized by two groups. Categorical variables will be summarized by frequencies and percentages. Quantitative variables are summarized by mean and standard error of mean (SEM) or median and inter-quartile range, whichever is appropriate. A Chi-squared test or Fisher exact test will be used to compare the distribution of categorical variables, while two-sample t test or non-parametric Mann-Whitney U test will be used to compare the mean or median of quantitative variables. In addition to Chi-square/Fisher exact test, a logistic regression model will be used to compare the proportion of patients with the presence of at least mild bleeding between two groups. The analysis will be adjusted for the degree of obstruction and for other influential covariates in a multivariable logistic regression model. In addition, an ordinal logistic regression will be used to compare the severity of bleeding between two groups as long as the assumption of proportional odds met. Otherwise, a multinomial logistic regression model will be used for this purpose. The same analytical procedures will be used to compare the presence and the degree of impingement between two groups. Once again, univariable and multivariable logistic regressions will be used to compare Postoperative epistaxis and the presence of the extubation croup between two groups. Kaplan Meier survival plot and log rank test will be used to compare the distribution of time to discharge from the PACU. All tests are two-tailed at the level of significance of 0.05. The statistical software SAS, version 9.3 will be used for analyses.

Possible Discomforts and Risks: None beyond those incurred by standard practice

Possible Benefits: Identifying an easily implementable measure to reduce mucosal trauma and pain in children requiring NTL

Conflict of interest: Nothing to disclose

References:

- 1) Thermosoftening treatment of the nasotracheal tube before intubation can reduce epistaxis and nasal damage. Kim YC¹. Lee SH, Noh GJ, Cho SY, Yeom JH, Shin WJ, Lee DH, Ryu JS, Park YS, Cha KJ, Lee SC. *Anesth Analg*. 2000 Sep;91(3):698-701.
- 2) A silicone-based wire-reinforced tracheal tube with a hemispherical bevel reduces nasal morbidity for nasotracheal intubation. Kihara S¹, Komatsuzaki T, Brimacombe JR, Yaguchi Y, Taguchi N, Watanabe S. *Anesth Analg*. 2003 Nov;97(5):1488-91.

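### The logistic regressions planned for PACU epistaxis and croup have no sparse-event method or covariate limit, which puts their odds ratios and adjusted analyses at risk if events are few (low priority)

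*Combined protocol and SAP*

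**What the plan says.** Two of the secondary outcomes are binary events in the recovery unit. The first is "Postoperative epistaxis as defined as ongoing nasal bleeding in the recovery unit (PACU"), which the Postop paragraph calls persistent. The second is "presence of post-extubation croup in the PACU". The Data Analysis section states that "univariable and multivariable logistic regressions will be used to compare Postoperative epistaxis and the presence of the extubation croup between two groups". It does not list the covariates for these models. For the primary outcome, the adjustment set is degree of obstruction plus other influential covariates that are not named.

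The same section has a general provision that categorical variables will be compared by a chi-squared or Fisher exact test. For the primary outcome it says explicitly that logistic regression comes on top of those tests. It does not repeat this for the PACU outcomes. It gives a fallback if the proportional-odds assumption fails, but none for a binary model with too few events.

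The sample size is 40 per arm: "A sample size of 80 patients (40 in each group) can detect the difference of the same magnitude", meaning 27.5% against 7.5%. Those rates are for the presence of bleeding and were used to size the primary outcome. No rate is given for PACU epistaxis or croup.

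**The concern.** Ordinary logistic regression has no finite maximum-likelihood odds ratio when one arm has no events. With 40 per arm and an uncommon outcome, that is a realistic result. It would also occur in trials where the Parker arm has no PACU epistaxis at all, which is the result most favourable to the study tube. The analyst would then have to choose a substitute after seeing the data.

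An open covariate list adds to the problem. With a handful of events, an unrestricted multivariable fit is unstable. Even when it converges, it tends to overstate the odds ratio.

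**Working it through.** The plan gives no figure for these two outcomes to reproduce. Its only performance figure, power above 98%, is for the primary outcome. The plan's own inputs (40 per arm, 27.5% against 7.5%, two-sided 0.05) give about 66% by the pooled normal approximation. That is a separate matter, and nothing below depends on it.

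**Inputs from the documents.** n = 40 per arm; bleeding rates of 27.5% (control) and 7.5% (Parker), from the Power and Sample Size Justification.

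**Assumptions.** PACU epistaxis is taken as a fraction f of intubation bleeds, the same in both arms, because the outcome is defined as ongoing bleeding. Croup is given an equal rate in both arms. Neither f nor the croup rate is in the documents, so a range is shown.

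**Expected events at full persistence.** 40 × 0.275 = 11 and 40 × 0.075 = 3, so 14 in total.

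**Probability that at least one arm has no events.** P = 1 − [1 − (1 − pC)^40] × [1 − (1 − pT)^40], with pC = 0.275f and pT = 0.075f.

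| f | pC, pT | Expected events | (1 − pC)^40 | (1 − pT)^40 | P |
|---|---|---|---|---|---|
| 1.00 | 0.275, 0.075 | 14 | <0.001 | 0.044 | 4% |
| 0.75 | 0.20625, 0.05625 | 10.5 | <0.001 | 0.099 | 10% |
| 0.50 | 0.1375, 0.0375 | 7 | 0.003 | 0.217 | 22% |
| 0.25 | 0.06875, 0.01875 | 3.5 | 0.058 | 0.469 | 50% |

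Almost all of this probability comes from an empty Parker arm.

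**Croup, equal rate p in both arms.** P = 1 − [1 − (1 − p)^40]².
- p = 2%: 0.98^40 = 0.446, so P = 69%.
- p = 5%: 0.95^40 = 0.129, so P = 24%.
- p = 10%: 0.90^40 = 0.015, so P = 3%.

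**What survives a zero cell.** Fisher's exact test still returns a p-value: 5 against 0 of 40 gives 0.055, and 6 against 0 gives 0.026. It has nothing to compare only when neither arm has an event. For croup that has probability 0.446² = 0.20 at 2% and 0.129² = 0.02 at 5%.

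**The choice of test matters.** For 5 against 0, the likelihood-ratio test from the logistic model gives p = 0.007, against 0.055 from Fisher. The two fall on opposite sides of 0.05, and the plan does not say which one decides.

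**Adjusted model at the 14-event ceiling.** The true log odds ratio is ln[(0.075/0.925)/(0.275/0.725)] = −1.54. In simulation with several assumed covariates, the ordinary fit averaged about −1.75 and the Firth fit about −1.51. The exact gap depends on the covariates assumed.

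**The case against.** The strongest reply is that the plan already covers the comparison. The chi-squared or Fisher provision applies to categorical variables generally, and both outcomes are binary. The sentence on PACU outcomes reads as continuing the layered approach used for the primary outcome, and nothing in it displaces the general provision. This stands. A reader might infer that these outcomes could not be analysed as planned, but the documents do not support that: an unadjusted p-value remains available.

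Three other stronger readings also fail.
- A reader might take it as established that events will be few. The documents give no PACU rates. The 14-event ceiling is an inference from the word ongoing, and neither definition requires bleeding recorded at intubation. At rates of 10% or more in both arms, a zero-event arm is rare (3% or less at equal rates).
- A reader might infer that adjusting for adenoid size makes the tube comparison fail far more often. An adenoid level without events makes only that level's coefficient infinite. The tube-group odds ratio stays finite unless an arm is empty, so its failure rate is essentially the univariable one: in simulation with an assumed three-level adenoid factor, 50% at f = 0.25 and 22% at f = 0.50.
- A reader might infer that the plan commits to an uninformative Wald p-value. It names no Wald test. The likelihood-ratio test stays defined at a zero cell, though it is liberal with sparse counts (type I error of about 9% at 5% croup).

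The reply does not supply a method for the odds ratio and its interval when an arm is empty, or a limit on the covariates.

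**Conclusion.** The point holds in a limited form. The plan relies on ordinary logistic regression for two potentially sparse outcomes and says nothing about what replaces it if the fit fails. The odds ratio, its confidence interval and the adjusted analysis are exposed; the unadjusted test is not.

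For PACU epistaxis, the chance of a non-finite tube-group odds ratio runs from 4% to 50% as assumed persistence falls from 100% to 25%. For croup it runs from 3% to 69% as the assumed rate falls from 10% to 2%. The epistaxis figures rest on treating PACU epistaxis as a subset of intubation bleeding with equal persistence in both arms. The croup rates have no anchor in the documents.

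Both outcomes are secondary and neither affects the primary conclusion. This is a cheap improvement of low priority.

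**What to change.** In the Data Analysis section, for PACU epistaxis and post-extubation croup:
- State that Fisher's exact test is the comparison, reported with event counts per arm and an exact 95% confidence interval for the risk difference. Both remain usable when one arm has no events.
- Replace the unrestricted multivariable model with Firth-penalised (or exact) logistic regression containing tube group and adenoid-size stratum only. Adenoid size is the stratification factor, so it is the natural covariate to keep.

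The cost is SAP wording only, with no change to patients, visits or data collected. The downside is fewer covariates in the adjusted model for two secondary outcomes.

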16) Nasotracheal fiberoptic intubation: a randomised controlled trial comparing the GlideRite® (Parker-Flex® Tip) nasal tracheal tube with a standard pre-rotated nasal RAE™ tracheal tube. Lomax SJ¹, Johnston KD, Marfin AG, Yentis SM, Kathawar QQ, Popat MT, Anaesthesia. 2011 Mar;66(3):180-4. doi: 10.1111/j.1365-2044.2011.06621.x.

17) EFFECTS ON POSTOPERATIVE SORE THROATS OF TWO ANALGESIC AGENTS AND LUBRICANTS USED WITH ENDOTRACHEAL TUBES. LUND LVII, DAQS FG, Anesthesiology. 1965 Sep-Oct;26:681-3. -need full text article to confirm

(*)

Cuffed NTT size selection chart based on the formula (age+16)/4 - 0.5 (rounded to nearest size) with exceptions for children with Trisomy 21 (tube down-sized by 1), and in the case of severe impingement (tube down-sized by 0.5)

Patient age (yrs)	NTT size, cuffed	NTT size, cuffed, children with Trisomy 21	NTT size, cuffed, in case of severe impingement	NTT size, cuffed, in children with Trisomy 21, in case of severe impingement
3-4	4.5	4.0	4.0	3.5
5-6	5.0	4.5	4.5	4.0
7-8	5.5	5.0	5.0	4.5
9-10	6.0	5.5	5.5	5.0
11	6.5	6.0	6.0	5.5
